#### 3.1 Efficacy endpoints

#### 3.1.1 Primary efficacy endpoint

The primary efficacy endpoint of the study is the change from baseline to Week 12 in the number of BE days per week.

A "BE day" is a day in which at least one confirmed BE episode occurred [see Section 7.2.4.1].

ACT-539313	
Binge Eating Disorder	
Protocol ID-082A201	Confidential
Final Version 3	
4 May 2021, page 39/140	

A BE episode is defined as "eating, in a discrete period of time (e.g., within any 2-hour period), an amount of food that is definitely larger than most people would eat in a similar period of time under similar circumstances" (as defined in the DSM-5 criteria) [APA 2013]. In addition, a BE episode is characterized by "a sense of lack of control over eating during the episode (e.g., a feeling that one cannot stop eating or control what or how much one is eating)".

Throughout the study, from Screening to Week 12, study participants record each BE episode they experience on a diary card that is filled in daily. At randomization and at each subsequent study visit, the investigator reviews the diary entries with the study participant to determine whether a recorded episode fulfilled criteria for a BE episode and to ascertain if there were other unrecorded BE episodes during the preceding interval. The investigator records in the eCRF the BE episodes that have been confirmed. In the eCRF, every day must be described as either having an entry (0 or x number of BE episodes) or not having an entry (missing data).

The "number of BE days per week at baseline" is calculated as the number of BE days from Day -14 to Day -1 divided by the number of days with diary entries in this period and multiplied by 7. A minimum of 6 entries for each of the 2 weeks preceding randomization is required per inclusion criteria to ensure study participant compliance with filling in the BE diary.

The "number of BE days per week" during the study, from randomization up to Week 12, is calculated as the number of BE days over a 2-week period divided by the number of days with diary entries in this period and multiplied by 7. A minimum of 7 diary entries per 14-day time interval is required [see Section 9.2.2.1]. The last calculation, covering Weeks 11 and 12, will be used for the primary endpoint.

All calculations will be done by the sponsor; the calculations at baseline should also be done by the investigator as part of the eligibility assessment, as per Section 7.2.3. The sponsor may collect the original diaries for data reconciliation.

# 3.1.2 Exploratory efficacy endpoints

Exploratory efficacy endpoints are listed in Table 2.

# 3.2 Safety endpoints

Safety endpoints are listed in Table 2.

# 3.3 Pharmacokinetic endpoints

ACT-539313 plasma concentrations will be measured prior to the morning dosing at Week 4, Week 8, and Week 12 to determine individual trough concentrations and the possible influence of various covariates thereupon. Population PK parameter estimates

ACT-539313		Doc No D-21.148
Binge Eating Disorder		
Protocol ID-082A201	Confidential	
Final Version 3		
4 May 2021, page 40/140		

may also be evaluated on an exploratory basis. Plasma samples may also be used by Idorsia Preclinical Pharmacokinetics and Metabolism department for exploratory assessments of circulating metabolites of ACT-539313.

# **3.4** Appropriateness of endpoints

The assessment of the change in the number of BE days per week as an endpoint has been accepted by the FDA, supporting approval of other therapies in this indication. The FDA review of the lisdexamfetamine dimesylate dossier [FDA 2015], discussing the adequacy of weight loss as primary endpoint in BED, did not consider weight loss as a suitable primary endpoint for this disease: "... primary efficacy endpoint is most important information for clinicians, and for patients with BED (reducing binge eating days), and so the emphasis in labeling should be on the psychiatric aspects of the disorder...".

A change in BED may be assessed either by a reduction in the frequency of BE episodes or by a reduction in the frequency of BE days. The frequency of BE episodes is a good descriptor of disease severity and it allows the reduction in severity for study participants not reaching remission to be assessed. In patients with severe BED, if the reduction in episode frequency is large enough it could lead to a meaningful benefit. With lisdexamfetamine dimesylate, treatment effects were observed consistently across several BE-related endpoints including BE episodes and BE days, reinforcing the clinical relevance of both endpoints [McElroy 2017b]. Similar conclusions were drawn in clinical trials with topiramate [McElroy 2007] and sibutramine [Wilfley 2008].

Attitudinal and behavioral dimensions of the eating psychopathology in BED will be assessed by the change from baseline to Week 12 in the EDE-Q 7-item scale global score and subscale scores on dietary restraint, shape/weight overvaluation, and body dissatisfaction.

BED shares many characteristics with addictive behaviors, e.g., diminished control, continued food intake despite negative consequences [Gearhardt 2012], and with obsessive-compulsive symptoms (or features) in that symptoms are intrusive, time consuming, distressing, potentially inhibit or hinder functioning, and may or may not be successfully resisted [Deal 2015]. The study will also assess the efficacy of the drug on disease-specific obsessive and compulsive symptoms by using the YBOCS-BE [Goodman 1989, Deal 2015].

The study will use the CGI-S/C as well as the PGI-S/C scales to assess the global impression of disease related to severity and change from a clinician and patient perspective.

Anxiety and depression are common comorbidities in BED [Guerdjikova 2017]; the study will use HAMD-17 to assess symptoms of anxiety and depression.

ACT-539313 Binge Eating Disorder Protocol ID-082A201 Final Version 3 4 May 2021, page 41/140

Confidential

In summary, all efficacy assessments have been well documented and regarded as reliable, accurate and relevant in this patient population.

# **4 STUDY DESIGN AND PLAN**

# 4.1 Study design

This is a Phase 2, multicenter, double-blind, randomized, placebo-controlled, parallel-group, proof-of-concept study assessing ACT-539313 at a dosing regimen of 100 mg b.i.d. vs placebo over a 12-week treatment period in adult participants with moderate to severe BED.

The study treatment will be taken in the morning at breakfast and in the evening at dinner.

This study will randomize approximately 120 participants to either ACT-539313 at a dose of 100 mg b.i.d., or placebo in a 1:1 ratio.

# 4.1.1 Study periods for an individual study participant

The study comprises the following consecutive periods:

**Screening period:** Lasts a minimum of 14 days and up to 28 days; starts with the full signature (study participant, investigator/delegate) of the ICF and ends with the study participant's randomization or screening failure.

**Treatment period:** Starts with the administration of the first dose of study treatment and ends on the day of the last dose of study treatment. The study participants will be treated for 12 weeks.

**Safety follow-up period:** Starts on the day after the last dose of study treatment and ends at the EOS visit ( $10 \pm 3$  days after EOT).

Participation in the study ends with the completion of the EOS visit [Table 1]. The duration of participation in the study of a study participant is expected to be up to 128 days.

The visit schedule and protocol-mandated procedures are performed according to the schedule of activities [Table 1] and are described in Section 7.2.

The overall study design is depicted in Figure 1.

# 4.2 Study duration and global End-of-Study definition

The study starts with the recruitment of the first study participant. A study participant is considered recruited when the study participant's ICF has been fully signed.

ACT-539313		Doc No D-21.148
Binge Eating Disorder		
Protocol ID-082A201	Confidential	
Final Version 3		
4 May 2021, page 42/140		

The study primary completion date is the date of the last study participant's EOT visit.

The global EOS is defined as completion of the EOS visit of the last study participant. The study is expected to last approximately 14 months.

# 4.3 Study design rationale

The proposed clinical study ID-082A201 has been designed based on previously conducted clinical studies in BED [McElroy 2017b, Wilfley 2008, FDA 2015] as well as data from the two ACT-539313 Phase 1 studies, AC-082-101 [D-18.013, D-20.035] and ID-082-102 [D-18.159]. This is the first clinical study to assess selective OX1R antagonism as a new mechanism of action in patients with eating disorders and to establish an initial signal for efficacy and to ensure safety. Based on the results of this study, ACT-539313 may be further investigated in a Phase 2 dose-finding study and in a confirmatory Phase 3 program in BED.

The DB, randomized, and placebo-controlled design minimizes the chance of bias in the implementation, execution, assessment, and interpretation of the effects of treatment. While there is a drug approved for BED (lisdexamfetamine), its status as a Schedule II controlled substance limits its use in this POC study as an active control.

A treatment duration of 12 weeks has been selected as this duration has been adequate to evaluate the benefit/risk of compounds tested in this indication [McElroy 2017b, FDA 2015]. In addition, it is unclear how long it would take for an OX1R antagonist to modulate the neuronal dysregulation of BED, leading to a reduction in the compulsive behavior that will then translate into a reduction in BE episodes. The 12-week duration is expected to provide an adequate time period to allow for both efficacy and safety data assessment.

# 4.4 Justification for dose

For this POC study, the dose of 100 mg b.i.d. was chosen to assess the effect of ACT-539313 on BED.

The selected dose of 100 mg b.i.d. is expected to cover the exposure to ACT-539313 that was necessary in a rat model to reduce BE by selective OX1R antagonism. Safety pharmacology and toxicity studies have demonstrated appropriate safety margins,

Single doses up to 400 mg and multiple doses up to 200 mg b.i.d. for 6.5 days have been tested in healthy male and female study participants, while a dose of 200 mg b.i.d. for up to 10 days has been tested in healthy male study participants. No safety issue of concern was detected as all AEs were transient and of mild or moderate intensity, and no

treatment-related effects on vital signs, clinical laboratory, or ECG variables were observed.

# 4.5 Study committee(s)

No study committee will be appointed for this study.

# **5 STUDY POPULATION**

# 5.1 Study participant population description

This study will enroll male and female participants aged 18–55 years (inclusive), with a diagnosis of BED in accordance with DSM-5 criteria. In addition, the disease severity should be at least moderate, defined in this study as having at least 4 BE episodes per week, on average, for a duration of at least 6 months.

To ensure proper application of the diagnostic criteria, the BED diagnosis section of the SCID-5 will be used at Screening. This is a semi-structured interview guide for making the major DSM-5 diagnoses. It is administered by a clinician or trained mental health professional who is familiar with the DSM-5 classification and diagnostic criteria. In addition, the EDE-Q will be completed at Screening to further confirm the diagnosis of BED, assess all dimensions of the eating psychopathology, as well as confirm the self-reported BED severity.

More details on inclusion and exclusion criteria follow below [see Sections 5.3 and 5.4].

# 5.2 Rationale for the selection of the study population

The rationale for selecting patients with at least moderate severity and longer duration of BE symptoms ( $\geq 6$  months) is that these patients are more likely to be impacted by the disease, more likely to seek treatment, and thus more likely to respond to the effects of a pharmacological intervention such as ACT-539313. In studies looking at both clinical and community samples, patients with moderate to severe BED, and especially those with overvaluation of weight/shape, were found to have greater eating-disorder psychopathology than patients with mild BED [Grilo 2015a, Grilo 2015b]. Patients with moderate to severe BED are often considered for pharmacotherapy as either monotherapy or in combination with behavioral treatment options.

Placebo response during clinical trials of medications for BED has been reported to range from 26% to 38%, with less severe eating pathology at baseline being associated with a higher placebo response [Blom 2014].

In comparison to other eating disorders, BED is distributed more broadly across age, sex, and racial/ethnic groups and no restrictions are made in this study with respect to these factors. However, in this initial POC study, an upper age limit of 55 years is included to increase the probability of detecting an efficacy signal as persistence of BED in older

individuals may be a sign of intractable BE and poorer response to treatment. Subsequent studies will allow a broader age range, beyond the 55 years limit.

#### 5.3 Inclusion criteria

Study participants must meet all the following inclusion criteria:

#### Criteria assessed at Visit 1:

- 1. Signed and dated informed consent form prior to any study-mandated procedure.
- 2. Male or female study participants aged 18 to 55 years at the time of signing the informed consent form.
- 3. BED in accordance with DSM-5 criteria diagnosed using the SCID-5.
- 4. Self-reported BED severity of at least moderate level, defined as at least 4 BE episodes per week, on average, for a duration of at least 6 months.
- 5. BED in accordance with EDE-Q.
- 6. CGI-S score of  $\geq 4$ .
- 7. For WOCBP [see definition in Section 5.5]:
  - Negative serum pregnancy test at Visit 1; and
  - Agreement to undertake monthly urine or serum pregnancy tests during the study and up to the EOS visit; and
  - Agreement to use an acceptable contraceptive method as described in Section 5.5.2.
- 8. Able to speak, read and understand English, to communicate well with the investigator, to understand the study requirements, and judged by investigator to be alert and oriented to person, place, time, and situation.

#### Criteria assessed at Visit 2:

- 9. Reporting  $\geq$  3 BE days for each of the 2 weeks prior to randomization as documented in the participant's BE diary and with BE diary entries completed for at least 6 days per week during this 2-week period (between Visit 1 and 2).
- 10. CGI-S score of  $\geq$  4.
- 11. For WOCBP: negative urine pregnancy test.

#### 5.4 Exclusion criteria

Study participants must not meet any of the following exclusion criteria:

#### Criteria assessed at Visit 1:

- 1. BMI <  $18.0 \text{ kg/m}^2 \text{ or} > 45 \text{ kg/m}^2$ .
- 2. Any acute or chronic-persistent psychiatric disorder (see also under 3 and 4 below) other than BED diagnosed in the past, including anorexia nervosa, bulimia, psychotic disorders, bipolar disorder, hypomania, dementia, as defined by the DSM-5 criteria or by the MINI©.
- 3. Episode(s) of major depressive disorder or any anxiety disorder occurring within the 6 months prior to Screening as defined by the DSM-5 criteria or by the MINI©; or currently taking, or has taken, any medication for depression or anxiety during the 3 months prior to Screening.
- 4. History of substance use disorder (including alcohol use disorder), excluding nicotine and caffeine, within the 12 months prior to Screening, as defined by the DSM-5 criteria or by the MINI©.
- 5. Any clinically unstable medical condition, significant medical disorder or acute illness that, in the investigator's opinion, could interfere with the participant's ability to comply with study assessments or abide by study restrictions.
- 6. History of malignancy within 5 years prior to the Screening visit, except for adequately treated basal cell or squamous cell skin cancer. History of pituitary tumor, whether benign or malignant, is exclusionary.
- 7. Presence of significant psychosocial or environmental stressors (e.g., loss of employment, loss of housing) or any factor that could impede participant's ability to adhere to protocol requirements, as judged by the investigator.
- 8. Participants whose work requires them to operate heavy-duty vehicles or other heavy or dangerous machinery.

Note: Participants must be cautioned on the potential risk of somnolence and it is recommended to refrain from engaging in hazardous activities that require complete mental alertness, including driving, following study treatment intake until fully alert and comfortable to do so [See also Section 5.7].

9. Use of any medications for the treatment of BED (including lisdexamfetamine [Vyvanse®]), any other eating disorder, obesity, or weight gain, or any other medication that could result in weight gain or weight loss, including over-the-counter and herbal products, within 3 months prior to Screening.

- 10. Any ECG findings of QTc prolongation or history of additional risk factors for torsade de pointes, which, in the opinion of the investigator, could affect the participant's safety or interfere with the study assessments.
- 11. Any abnormal hematology or biochemistry test results, which, in the opinion of the investigator, could affect the participant's safety or interfere with the study assessments.
- 12. AST and/or ALT >  $1.5 \times$  ULN and/or total/direct bilirubin >  $1.5 \times$  ULN and/or moderate to severe hepatic impairment defined as Child Pugh Score B or C.
- 13. Positive test for either hepatitis B surface antigen or hepatitis C antibody and AST and/or ALT and/or total bilirubin test results at Screening above the ULN for the reference laboratory.
- 14. Positive HIV test.
- 15. TSH level outside of the established reference range to an extent that is considered clinically relevant per investigator judgment. Participants diagnosed with hyper- or hypothyroidism who have been on therapy with a stable dose for at least 3 months prior to Visit 1 and are clinically and chemically euthyroid are allowed.
- 16. Current or previous participation in any clinical trial within the last 90 days, or participation in more than 2 clinical trials within the past year. This includes studies using marketed drugs or devices.
- 17. Psychological or behavioral weight-loss interventions for BED initiated during the 3 months prior to Screening or planned to be initiated during the study. A participant treated with those therapies is eligible if the therapy has been started at least 3 months prior to randomization and the participant agrees to keep it stable during the study.
- 18. Any history of bariatric surgery including gastric jejunal bypass, Roux-en-Y gastric bypass, sleeve gastrectomy, lap bands, duodenal stents, or other procedures for weight loss or planned to be performed during the study.
- 19. Treatment with CNS-active drugs, such as centrally active anticholinergics, sedating antihistamines, morphine and other opioids, anticonvulsants, antidepressants, anxiolytics, mood stabilizers, antipsychotics, stimulants, sleep drugs, anti-Parkinson's drugs, etc., within 30 days prior to Screening or planned to be initiated during the study.
- 20. Treatment with sensitive substrates of CYP3A4, moderate or strong inhibitors and/or inducers of CYP3A4, and sensitive substrates of CYP2C19, CYP2C8 and CYP2C9 within 2 weeks of randomization (Visit 2) or planned to be initiated during the study.

- 21. Consumption of the following fruits and their juices is not permitted within 2 weeks of randomization (Visit 2) to EOT visit: grapefruit, grapefruit hybrids, Seville orange, pomelos, pomegranates, and star fruits.
- 22. Use of medications that affect body weight or appetite, including weight loss medications, insulin, GLP-1 receptor agonists, systemic corticosteroids, over-the-counter (including herbal) medications, within 3 months prior to Screening or planned to be initiated during the study.
- 23. Known hypersensitivity to drugs of the same chemical/pharmacological class as ACT-539313, or any of its excipients.
- 24. Previous exposure to ACT-539313.

#### Criteria assessed at Visit 1 and Visit 2

- 25. HAMD-17 score  $\geq$  17 points at Visit 1 and/or Visit 2.
- 26. Any of the following conditions related to suicidality:
  - a) Participant is considered to have a suicide risk in the investigator's opinion or has a previous history of suicide attempt within the past 12 months.

b) Participant answers "yes" to "suicidal ideation" item 2 (non-specific active suicidal thoughts), item 3 (active suicidal ideation with any methods [not plan] without intent to act), item 4 (active suicidal ideation with some intent to act, without specific plan), or item 5 (active suicidal ideation with specific plan and intent) on the C-SSRS® assessment at Screening (in the past month). Participants who answer "yes" to this question must be referred to the investigator for follow-up evaluation.

- 27. Female participants: pregnant, lactating or planning to become pregnant during the projected course of the study.
- 28. Positive urine drug screen (for benzodiazepines, barbiturates, cannabinoids, opiates, amphetamines, phencyclidine, antidepressants or cocaine).

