### 2.1.2 Current treatment options

Treatment for BED includes a variety of approaches targeting the core behavioral features and psychological features of the disease. Psychological and behavioral approaches remain the mainstay of therapy and include cognitive behavioral therapy, interpersonal psychotherapy, and behavioral weight loss [Wilson 2011, Iacovino 2012, Steinberg 2014]. In January 2015, lisdexamfetamine became the first medication to receive US FDA approval for treating moderate to severe BED [Vyvanse® USPI]. Many other medications are used off-label, including antidepressants (selective serotonin reuptake inhibitors, serotonin–norepinephrine reuptake inhibitors, and bupropion), anticonvulsants (topiramate), and anti-obesity agents [McElroy 2017a, Citrome 2019]. ACT-539313 Binge Eating Disorder Protocol ID-082A201 Final Version 3 4 May 2021, page 33/140

Confidential

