#### 6.2.2 Forbidden concomitant therapy

Study participants must not be withdrawn from medically necessary therapies in order to participate in the study. These participants must rather be considered as non-eligible for the study due to their medical condition and their requirement for these therapies.

The following concomitant therapies are forbidden during the study:

• CNS-active drugs, such as centrally active anticholinergics, sedating antihistamines, morphine and other opioids, anticonvulsants, antidepressants, anxiolytics, mood

stabilizers, antipsychotics, stimulants, sleep drugs, and anti-Parkinson's drugs within 30 days prior to Screening or planned to be initiated during the study and until EOS.

- Medications that affect body weight or appetite, including weight-loss medications, insulin, GLP-1 receptor agonists, systemic corticosteroids etc., within 3 months prior to Screening and until EOT.
- Moderate and strong inducers and inhibitors of CPY3A4, sensitive substrates of CYP3A4, CYP2C19, CYP2C8, and CYP2C9 within 2 weeks prior to randomization (Visit 2) or planned to be initiated during the study and until 24 h after EOT.
- Any medications for the treatment of BE, including lisdexamfetamine (Vyvanse®), any other eating disorder, obesity, or weight gain, or any other medication that could result in weight gain or weight loss including over the counter and herbal products within 3 months prior to Screening.
- Psychotherapy or behavioral weight-loss interventions for BED during the study and until 24 h after EOT.

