Supplementary Estimand #2	Adult study participants with BED according to DSM-5, having at least 3 BE days per week, completing 12 weeks of treatment without use of other medication.	Change from baseline to Week 12 in the number of BE days per week.	Hypothetical, i.e., endpoint data after intercurrent event are not used.	Mean change from baseline for each treatment group. Treatment effect expressed as difference of LSMean changes from baseline (ACT-539313 minus placebo; from mixed model).

Intercurrent events are premature discontinuation of treatment and use of other, forbidden, medication for BE. BE = binge eating; BED = binge eating disorder; DSM-5 = Diagnostic and Statistical Manual of Mental Disorders (5th edition); LSMean = least squares mean.

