Estimand	Target Population	Endpoint	Strategy for addressing intercurrent events	Population- level summary
Supplementary Estimand #2	Adult study participants with BED according to DSM-5, having at least 3 BE days per	Change from baseline to Week 12 in the number of BE days per week	Hypothetical, i.e., endpoint data after intercurrent event are not used.	Mean change from baseline to Week 12 for each treatment group.

Treatment effect

completing expressed as 12 weeks of difference of treatment LSMean without use of changes from other baseline to medication Week 12 (ACT-539313 minus placebo; from mixed model)

week at baseline,

Intercurrent events are premature discontinuation of treatment and use of other, forbidden, medication for BE.

BE = binge eating; BED = binge eating disorder; DSM-5 = Diagnostic and Statistical Manual of Mental Disorders (5th edition); LSMeans = Least Squares Means.

In the choice of intercurrent events it was considered that, in symptomatic settings, it is not the usual practice to continue to assess effectiveness in subjects after they have stopped taking the assigned treatment [O'Neill 2012]. Also, if an alternative (or additional) drug is started, this could influence the outcome for a subject [O'Neill 2012]. Therefore, two types of intercurrent events were considered: premature discontinuation of double-blind treatment (ACT-539313 or placebo) and use of other forbidden medication for BE.

Excluding measurements obtained after an intercurrent event will lead to a hypothetical strategy estimand (ICH E9[R1]). A hypothetical strategy is related to the scenario in which the intercurrent events would not occur (i.e., all subjects completing the 12 weeks of assigned treatment without using forbidden BE medication), which is a reasonable approach for this proof-of-concept study.

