14.12 List of BE forbidden medication

Table 9BE forbidden medication

Medication	
lisdexamfetamine (Vyvanse)	
topiramate (Topamax)	
bupropion (Aplenzin, Forfivo, Wellbutrin)	
olanzapine (Zyprexa)	
fluoxetine (Prozac)	
other SSRIs such as citalopram, escitalopram, sertraline, paroxetine, fl	uvoxamine
SNRIS such as duloxetine, desvenlafaxine, venlafaxine	
other anticonvulsants such as zonisamide and lamotrigine	
bupropion-naltrexone (Contrave)	
liraglutide (Saxenda)	
orlistat (Alli, Xenical)	
phentermine-topiramate (Qsymia)	
setmelanotide (IMCIVREE)	
semaglutide (Wegovy)	
lorcaserin (Belviq)	
phentermine (Adipex-P. Suprenza)	
sibutramine (Meridia)	
benzphetamine	
diethylpropion	
phendimetrazine	

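### Starting psychotherapy or a behavioral intervention for BED is forbidden during the study but is not an intercurrent event, so diary data after such a start stay in the primary analysis

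*Protocol*

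**What the plan says.** **Intercurrent events.** Below Protocol Table 4 (Section 9.2.1) the definition reads: "Intercurrent events are premature discontinuation of treatment and use of other, forbidden, medication for BE". SAP 6.1.2 repeats it: "two types of intercurrent events were considered: premature discontinuation of double-blind treatment (ACT-539313 or placebo) and use of other forbidden medication for BE". Both apply a hypothetical strategy, under which endpoint data after the event are not used. The SAP describes the imagined scenario as "all subjects completing the 12 weeks of assigned treatment without using forbidden BE medication". SAP 6.1.7 points to Section 14.12 (Table 9) for the forbidden BE medications, and every entry there is a drug or drug class.

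**Rules on non-drug therapy.** Protocol 6.2.2 includes among the forbidden concomitant therapies: "Psychotherapy or behavioral weight-loss interventions for BED during the study and until 24 h after EOT". Exclusion criterion 17 keeps out people with "Psychological or behavioral weight-loss interventions for BED initiated during the 3 months prior to Screening or planned to be initiated during the study", but admits those already in such therapy for at least 3 months who agree to keep it stable. On the place of these treatments, Protocol 2.1.2 says: "Psychological and behavioral approaches remain the mainstay of therapy".

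**Data collected.** Protocol 7.2.2 has all concomitant medication and non-pharmacological therapy recorded in the eCRF.

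**The concern.** The SAP justifies its second intercurrent event by noting that an alternative or additional drug could affect a participant's result. That argument applies at least as well to a newly started psychological or behavioral treatment, which the protocol itself ranks ahead of drugs. The plan nevertheless treats the two differently: data after a forbidden BE drug are set aside, while data after a forbidden BED psychotherapy are kept and attributed to the assigned arm. In effect the primary estimand is hypothetical for drugs and treatment-policy for psychotherapy, and neither document states or defends the second choice.

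At stake is the meaning of the primary estimate. A sponsor reading it as the effect of ACT-539313 without other BED treatment would be reading something slightly different if starts were unequal between arms.

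**Working it through.** **1. The two kinds of forbidden therapy compared**

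| Therapy started after randomization | Forbidden? | Intercurrent event? | Later diary data in the primary model |
|---|---|---|---|
| BE drug in SAP Table 9 | Yes, Protocol 6.2.2 | Yes | Excluded |
| Psychotherapy or behavioral intervention for BED | Yes, Protocol 6.2.2 | No | Kept |

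The word medication cannot be stretched to cover psychotherapy: Protocol 6.2 and 7.2.2 name medication and non-pharmacological therapy as separate things, and Table 9 has no non-drug entry.

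**2. Whether another planned analysis closes the gap**

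- *Per-protocol set.* It may remove some cases through a separate deviation document (SAP 4.1.4), but it removes the whole participant. SAP Table 2 makes its efficacy use conditional on a size difference above 10% from the FAS, whereas SAP 6.1.7 states the repeat without a condition.
- *Supplementary Estimand #2.* It refers only to other medication.
- *All-data repeat (SAP 6.1.7).* It restores data after the two listed events, so it does not isolate this one.
- *Jump-to-reference and tipping point (SAP 6.1.6).* These replace missing values; the data at issue are observed.

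None of them changes the primary FAS analysis.

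**3. The plan's own sample-size figures**

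Inputs from Protocol 9.4: two-sided 0.05, 1:1 allocation, effect size 0.6.

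- Per arm, n = 2(1.960 + 1.282)² / 0.6² = 58.4, rounded up to 59, so 118 in total. Table 5 says 118.
- At 60 per arm, power = Φ(0.6 × √30 − 1.960) = Φ(1.326) = 90.8%. Table 6 says 91%.

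The remaining cells of both tables also reproduce. No stated figure is in dispute.

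**4. Size of the bias**

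Let p_P and p_A be the proportions starting therapy on placebo and on ACT-539313, g the extra reduction in BE days per week at Weeks 11–12 among starters (same in both arms), and Δ the true reduction against placebo.

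Estimated difference = Δ − (p_P − p_A) × g

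The documents give Δ = 1 and SDs of 1.6 and 2.0 (Protocol 9.4). They give neither p_P, p_A nor g, so the values below are assumptions. Power is from a two-sample t-test with 60 per arm.

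| Excess on placebo | g | Bias | Estimated difference | Power, SD 1.6 | Power, SD 2.0 |
|---|---|---|---|---|---|
| 0 | any | 0 | 1.00 | 92.4% | 77.5% |
| 5 points | 1 | 0.05 | 0.95 | 89.7% | 73.3% |
| 5 points | 2 | 0.10 | 0.90 | 86.3% | 68.6% |
| 10 points | 1 | 0.10 | 0.90 | 86.3% | 68.6% |
| 10 points | 2 | 0.20 | 0.80 | 77.5% | 58.4% |
| 15 points | 1 | 0.15 | 0.85 | 82.3% | 63.6% |
| 15 points | 2 | 0.30 | 0.70 | 66.2% | 47.7% |

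With 60 per arm, 5, 10 and 15 points are 3, 6 and 9 more starters on one arm than on the other. If the excess were on ACT-539313, the sign would reverse and the same assumptions would give 1.05 to 1.30. For scale, the standard error of the difference at SD 1.6 is 1.6 × √(2/60) = 0.29, so the range 0.05 to 0.30 is about 0.2 to 1.0 standard errors.

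**The case against.** **A deliberate choice.** The SAP explains how it chose its intercurrent events, and a treatment-policy approach to a rare, prohibited therapy would be legitimate in a proof-of-concept trial. That is fair, and such a choice could stand if it were stated and justified. It is not stated, and the reason the SAP does give does not separate drugs from psychotherapy.

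**Starts may be few and weak in effect.** Criterion 17 excludes anyone planning to start. Protocol 2.1.3 describes these treatments as costly and often hard to obtain, with about half of patients not responding fully. Any gain must show in study days 71–84, and participants who stop study drug already have their later data excluded. All of this stands: the real bias may be close to zero.

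**The events are not invisible.** A reader might infer from the drug-dictionary coding in SAP 5.3.4 that non-drug starts go unreported. The documents do not support that. A start breaches Protocol 6.2.2, and SAP 5.2 summarises deviations by category and treatment group and lists them. What is missing is a count specific to this therapy.

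**The per-protocol set may catch them.** The deviation document was not available for this review, so this can be neither confirmed nor ruled out. It would not alter the primary analysis.

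**Conclusion.** The concern holds as an inconsistency in the definition of the primary estimand. A forbidden therapy that the protocol regards as central to BED care is left outside the intercurrent events, for no stated reason, and later data stay in the FAS model. The magnitude is unknown; 0.05 to 0.30 BE days per week is an illustration that rests wholly on an assumed 5 to 15 point imbalance and an assumed gain of 1 to 2 days, equal in both arms and fully present at Weeks 11–12.

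Two stronger readings are tempting and should not be adopted:

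- *That the bias runs toward no effect.* It is plausible that participants without benefit seek therapy and that more of them are on placebo, but neither document reports starts by arm. Equal starts with equal gain cancel, and an excess on ACT-539313 would overstate the effect.
- *That SAP Table 9 is also defective because it names only two GLP-1 receptor agonists while criterion 22 bars the class.* Criterion 22 also covers insulin and systemic corticosteroids, which Table 9 omits. Table 9 lists BE medications and is not a copy of that criterion.

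**What to change.** Before unblinding:

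1. In SAP 6.1.2 and Table 3, and in Protocol Table 4 if it is amended, add the start after randomization of a psychological or behavioral intervention for BED as a third intercurrent event under the existing hypothetical strategy.
2. Exclude BE-day and BE-episode data from the start date, using the non-pharmacological therapy recorded in the eCRF. The existing minimum of 7 entries per 14-day window can decide whether a partly affected window is still usable.
3. Report the number of such starts by treatment arm.
4. Reconcile criterion 17 with Protocol 6.2.2. The former lets stable earlier therapy continue; the latter bans psychotherapy and behavioral weight-loss interventions during the study without that exception. Criterion 17 also counts its 3 months from Screening in one sentence and from randomization in the next. Until these agree, the event cannot be defined without ambiguity.

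A change in an already stable therapy should not be a trigger unless the eCRF is shown to capture it; Protocol 7.2.2 establishes only that use is recorded.

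The cost is SAP wording, one derivation and one count. The downside is small: a few diary windows after the event are no longer used.
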